18.7.3. Tuberculosis Screening and Chest X-Ray

Screening TB results and chest X-rays will be listed. Results of TB questionnaires will also be listed.

19. Efficacy-RELATED BIOMARKERS

Value and change from Baseline in level of FCP, hs-CRP, and lymphocyte counts at protocol-specified visits will be summarized by visit and treatment for the FAS. Additionally, percent of change from Baseline in lymphocyte counts will also be summarized. Change from Baseline in these biomarkers to Week 12 of ADP334-302 and all scheduled visits up to Week 52 in APD334-308 will also be summarized using descriptive statistics (n, mean, SD, median, minimum, and maximum). Additionally, the following summaries will be provided for biomarker data:

- Line plots over time for mean with 95% CI for the following laboratory assessments:
 - Change from Baseline in lymphocytes
 - Percent change from Baseline in lymphocytes
 - Change from Baseline in hsCRP
 - Change from Baseline in FCP

The exploratory efficacy-related biomarker analyses for immunophenotyping, proteomics, RNA transcriptomics, and fecal microbiome will be described in a separate biomarker analysis plan.

20. Pharmacokinetics

PK samples to access plasma etrasimod concentrations will be collected prior to dosing (trough) at Weeks 16, 20, 24, 32, 40, 48, and 52; and at 2-Week and 4-Week Follow-Up visits for subjects that do not enroll into any extension study. A descriptive summary of observed plasma etrasimod concentration will be displayed by time and treatment group. Summary of observed plasma

etrasimod concentrations by time and treatment group will be repeated by sex (male or female), weight (\leq Median or $>$ Median) and age group ($<$ 18, 18 to $<$ 65, or \geq 65 years). Concentrations below the limit of quantitation (BLQ) will be assigned a numerical value of zero for the calculation of descriptive statistics. For geometric mean and geometric % coefficient of variation [CV], the zero values will be excluded.

The pharmacokineticist will determine the strategy for dealing with data affected by protocol deviations or events which may impact the quality of etrasimod concentration data on a case-by-case basis with input from the Arena study physician and Arena clinical pharmacologist, as needed. Examples for protocol deviations or events include, but may not be limited to, sample processing errors that lead to inaccurate bioanalytical results, and/or inaccurate dosing prior to PK sampling. In the case of an important protocol deviation or event, the affected PK data collected may be excluded from the summaries, calculation of the average steady-state trough plasma concentration ($C_{\text{trough,ss}}$) based on Week 16 to Week 52 trough concentrations ($C_{\text{trough,ss,W16-W52}}$), and population PK analysis, but will be reported in the study result listings.

Individual subject etrasimod plasma concentrations (and etrasimod metabolite concentrations, if applicable) will be presented in the data listings, including subject ID, treatment received, sex, age, weight, tobacco use, nominal timepoint, actual blood collection date/time, concentration, and time since last dose and also summarized using descriptive statistics (n, mean, SD, % CV, geometric mean, geometric % CV, median, minimum, and maximum) by nominal timepoint.

Individual subject steady-state trough (predose) plasma concentration will be averaged across Weeks 16 to 52 ($C_{\text{trough,ss,W16-W52}}$) and presented in a data listing and summarized using descriptive statistics.

Mean (\pm SD) etrasimod concentration versus nominal time (Weeks 16 to 52) will be plotted on linear scales. Plot will be repeated by sex (male and female).

Individual subject plasma etrasimod concentrations versus actual time (Weeks 16 to 52) will be plotted on linear scale.

Scatter plots of individual subject average steady-state $C_{\text{trough,ss,W16-W52}}$ versus Baseline body weight as a continuous variables will be generated for the Pharmacokinetic Set, which will also include the Spearman's rank correlation coefficient, p-value, and locally estimated scatterplot smoothing (LOESS) trend line.

Furthermore, the following overlay plots will be generated for the Pharmacokinetic Set within the etrasimod group only:

- Mean (SD) absolute lymphocyte counts and mean (SD) etrasimod concentration versus nominal timepoint (Weeks 16 through 52)
- Mean (SD) absolute change from Baseline in lymphocytes and mean (SD) etrasimod concentration versus nominal timepoint (Weeks 16 through 52)
- Mean (SD) percent change from Baseline in lymphocytes and mean (SD) etrasimod concentration versus nominal timepoint (Weeks 16 through 52)

- Mean (SD) heart rate and mean (SD) etrasimod concentration versus nominal timepoint (Weeks 16 through 52)
- Mean (SD) absolute change from Baseline in heart rate and mean (SD) etrasimod concentration versus nominal timepoint (Weeks 16 through 52)

The plasma etrasimod concentrations over time will be used in a population PK analysis, etrasimod concentration and specific efficacy endpoints will be used in a population PK/PD exposure-efficacy response analysis and etrasimod concentration and absolute lymphocyte count will be used in a population PK/PD exposure-lymphocyte response analysis, which will be described in a separate plan.

CCI

22. References

FDA. (2020) *Statistical considerations for clinical trials during the COVID-19 public health emergency*. U.S. Department of Health and Human Services, Food and Drug Administration. Guidance for Industry Web site. <https://www.fda.gov/media/139145/download>.

ICH. (2019) *Addendum on estimands and sensitivity analysis in clinical trials to the guideline on statistical principles for clinical trials, E9(R1)*. Retrieved from International Council for Harmonisation of Technical Requirements for Registration of Pharmaceuticals for Human Use: https://database.ich.org/sites/default/files/E9-R1_Step4_Guideline_2019_1203.pdf.

ICH. (2012) *Structure and content of clinical study reports questions & answers (R1)*. https://database.ich.org/sites/default/files/E3_Q%26As_R1_Q%26As.pdf.

ICH. (1998) *Statistical principles for clinical trials, E9*. Retrieved from International Council for Harmonisation of Technical Requirements for Registration of Pharmaceuticals for Human Use: https://database.ich.org/sites/default/files/E9_Guideline.pdf.

ICH. (1995). *Structure and content of clinical study reports, E3*. Retrieved from International Conference on Harmonisation of Technical Requirements for Registration of Pharmaceuticals for Human: https://database.ich.org/sites/default/files/E3_Guideline.pdf.

Ware, M. K. (2001). How to score version 2 of the SF-36 health survey (standard & acute forms). *Quality Metric Incorporated*.

APPENDIX 1. PROGRAMMING CONVENTIONS FOR OUTPUTS

IQVIA OUTPUT CONVENTIONS

Outputs will be presented as shown in the Output shells.

DECIMALS AND PERCENTAGES

- If the original data has N decimal places, then the summary statistics should have the following decimal places:
 - Minimum and maximum: N
 - Mean (and LS Means), median: N + 1
 - SD or SE: N + 2
- Percentages will be reported to one decimal place. Where counts are zero, percentages will not appear in the output.

DATES & TIMES

Depending on data available, dates and times will take the form DDMMYY or DDMMYY:hh:mm..

SPELLING FORMAT

English US.

PRESENTATION OF TREATMENT GROUPS

For outputs, treatment groups will be represented as follows and in the given order:

Treatment Group	For Tables, Graphs, and Listings
Etrasimod 2 mg	Etrasimod 2 mg
Placebo	Placebo
Screen Failure	Screen Failure
Not Treated ^a	Not Treated

^a To be used for subjects in safety listings who are randomized but do not receive study drug.

PRESENTATION OF VISITS

For outputs, visits will be represented as follows and in that order:

Visit Name	Study Period
Eligibility Assessment	Screening
Baseline, Week 12, Week 16, Week 20, Week 24, Week 32, Week 40, Week 48, and Week 52	Treatment
Early Termination	Dependent on Analysis Visit assigned
2-Week Follow-Up, 4-Week Follow-Up	Follow-Up

LISTINGS

All listings will be ordered by the following (unless otherwise indicated in the template):

- Randomized treatment group (or treatment received if it's a safety output), first by Etrasimod, then Placebo, then Not Randomized and then No Treatment (only in safety listings if there are any randomized subjects who did not receive study drug)
- Subject ID,
- Date (where applicable),
- For listings where non-randomized subjects are included, these will appear in a category after the randomized treatment groups labeled 'Not Randomized'.

APPENDIX 2. PARTIAL DATE CONVENTIONS

Imputed dates will NOT be presented in the listings.

ALGORITHM FOR TREATMENT EMERGENCE OF ADVERSE EVENTS IN STUDY APD334-308:

START DATE	STOP DATE	ACTION
Known	Known/Partial/ Missing	If start date < study drug first dose date in APD334-308, then not TEAE If start date < study drug first dose date in APD334-308 AND event worsened (increase in severity) after first dose date in APD334-308, then TEAE If start date >= study drug first dose date in APD334-308, then TEAE
Partial, but known components show that it cannot be on or after study drug first dose date in APD334-308	Known/Partial/ Missing	Not TEAE
Partial, could be on or after study drug first dose date in APD334-308 OR Missing	Known	If stop date < study drug first dose date in APD334-308, then not TEAE If stop date >= study drug first dose date in APD334-308, then TEAE
	Partial	Impute stop date as latest possible date (i.e. last day of month if day unknown or 31st December if day and month are unknown), then: If stop date < study drug first dose date in APD334-308, then not TEAE If stop date >= study drug first dose date in APD334-308, then TEAE
	Missing	Assumed TEAE

START DATE	STOP DATE	ACTION

ALGORITHM FOR PRIOR / CONCOMITANT MEDICATIONS:

Start Date	Stop Date	Action
Known	Known	
If medication stop date < study med first dose date in APD334-308, assign as prior
 
If medication stop date \geq study med first dose date in APD334-308, assign as concomitant

	Partial	
Impute stop date as latest possible date (ie, last day of month if day unknown or 31st December if day and month are unknown), then:
 
If medication stop date < study med first dose date in APD334-308, assign as prior
 
If medication stop date \geq study med first dose date in APD334-308, assign as concomitant

	Missing	If medication stop date is missing could never be assumed a prior medication, assign as concomitant
Partial	Known	
Impute start date as earliest possible date (ie, first day of month if day unknown or 1st January if day and month are unknown), then:
 
If medication stop date < study med first dose date in APD334-308, assign as prior
 
If medication stop date \geq study med first dose date in APD334-308, assign as concomitant

	Partial	
Impute start date as earliest possible date (ie, first day of month if day unknown or 1st January if day and month are unknown) and impute stop date as latest possible date (ie, last day of month if day unknown or 31st December if day and month are unknown), then:
 
If medication stop date < study med first dose date in APD334-308, assign as prior
 
If medication stop date \geq study med first dose date in APD334-308, assign as concomitant

	Missing	
Impute start date as earliest possible date (ie, first day of month if day unknown or 1st January if day and month are unknown), then:
 
If medication stop date is missing could never be assumed a prior medication, assign as concomitant

Missing	Known	
If medication stop date < study med first dose date in APD334-308, assign as prior
 
Else assign as concomitant

Start Date	Stop Date	Action
	Partial	Impute stop date as latest possible date (ie, last day of month if day unknown or 31st December if day and month are unknown), then: If medication stop date < study med first dose date in APD334-308, assign as prior If medication stop date \geq study med first dose date in APD334-308, assign as concomitant
	Missing	Assign as concomitant

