18.1. Adverse Events

Adverse Events (AEs) will be coded using MedDRA (version 24.1). The version used to code AEs will be displayed in the analyses. Treatment emergent adverse events (TEAEs) are defined as AEs that started or worsened in severity on or after the first dose of study treatment in Study APD334-308.

An event that was on-going at end of APD334-302 will be reported in APD334-308 only if it became worsened (increase in severity) after the first dose of study treatment in Study APD334-308. In an integrated report combining APD334-302 and APD334-308 data, this event will be counted only once.

Refer to APPENDIX 2 for handling of partial dates for AEs for the purpose of assigning treatment-emergent flags. In the case where it is not possible to define an AE as treatment emergent or not, the AE will be classified as treatment emergent.

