18.1.1. All TEAEs

All TEAEs will be summarized by SOC and PT and presented by descending frequency in the etrasimod group. All AEs, regardless of treatment-emergent status, will be included in an AE listing. Additionally, a listing of other AE details as collected on the CRF will be presented.

Exposure-adjusted incidence rate (EAIR) of TEAEs will be summarized by SOC and PT. Exposure is defined as the sum of either time (year) from first dose in Study APD334-308 to the onset of first such event for those who experienced this AE in Study APD334-308, or time (year) from first dose in Study APD334-308 to last participation for those who did not experience this AE. The EAIR is calculated as the number of subjects with the AE divided by the total exposure in subject-years.

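### SAP Appendix 2 omits the worsening exception for carry-over adverse events whose partial start date must precede APD334-308, contradicting SAP 18.1 and its own known-start-date row

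*SAP*

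**What the plan says.** SAP Section 18.1 defines TEAEs as "AEs that started or worsened in severity on or after the first dose of study treatment in Study" APD334-308. For an event still ongoing at the end of the parent study, it adds that the event is reported in APD334-308 "only if it became worsened (increase in severity) after the first dose of study treatment in Study" APD334-308. Neither sentence depends on how complete the start date is. The section then refers to Appendix 2 "for handling of partial dates for AEs for the purpose of assigning treatment-emergent flags". Where status cannot be determined, "the AE will be classified as treatment emergent".

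The treatment-emergence table in SAP Appendix 2 handles start dates as follows.

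- **Known, before the first APD334-308 dose:** not a TEAE, with an exception: "AND event worsened (increase in severity) after first dose date in APD334-308, then TEAE".
- **Partial, described as** "Partial, but known components show that it cannot be on or after study drug first dose date in APD334-308": one action, Not TEAE, for a known, partial or missing stop date. There is no exception.
- **Partial and possibly on or after that dose, or missing:** decided on the stop date. The event is a TEAE unless it stopped before the dose, and a missing stop date is assumed to mean TEAE.

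SAP Section 18.1.1 states: "All AEs, regardless of treatment-emergent status, will be included in an AE listing".

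**The concern.** The missing day of an onset date says nothing about whether severity increased later. Yet under Appendix 2 that missing day alone changes a worsened carry-over event from TEAE to not TEAE.

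This is an extension study with long-term safety as a stated objective, and Section 18.1 itself foresees events carried over from the 12-week parent study. An event lost through this row would be missing from:

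- the SOC/PT summaries and the exposure-adjusted incidence rates (18.1.1);
- the severity and relationship tables (18.1.1.1, 18.1.1.2);
- the outputs for discontinuation (18.1.2), serious TEAEs (18.1.3), TEAEs leading to death (18.1.4) and special interest (18.1.5);
- the overview (18.1.6).

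Among the TEAEs that matter most, a serious event or one leading to discontinuation could be affected in the same way as a mild one.

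**Working it through.** The plan states no figure to reproduce. The check has two parts: run the decision table against the definition, then bound the size.

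**1. Decision table against definition.** Assume a first APD334-308 dose on 15 June 2021 and an event that worsened after it. Two stop dates were tried, 1 September 2021 and missing; the result was the same for both.

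| Start date as recorded | Section 18.1 | Appendix 2 as written | Appendix 2 with the exception added |
|---|---|---|---|
| 10 May 2021 | TEAE | TEAE | TEAE |
| May 2021, day missing | TEAE | **Not TEAE** | TEAE |
| 2020, day and month missing | TEAE | **Not TEAE** | TEAE |
| June 2021, day missing (could be on or after) | TEAE | TEAE | TEAE |
| Missing | TEAE | TEAE | TEAE |

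The conflict is confined to one row of Appendix 2. When the same start dates were run for an event that did not worsen, adding the exception changed nothing. In particular, unworsened events in the disputed row stay Not TEAE, as Section 18.1 requires.

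**2. Does anything else in the SAP recover the event?** The fallback in Section 18.1 covers only events whose status cannot be determined. Here Appendix 2 determines it, so the fallback does not apply.

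**3. Size.** The documents give no count of carry-over events, partial dates or worsening. Every rate below is an assumption.

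- Events affected = carry-over events × share with partial start dates × share that worsened.
- Low: 20 × 0.05 × 0.10 = 0.10.
- High: 30 × 0.05 × 0.30 = 0.45.
- These figures are before removing partial dates that fall in the row for a possible start on or after the dose, which is not in error for worsened events.

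For the weight of one event, Protocol 10.2 gives approximately 35 Japanese subjects in the parent study and Protocol 6.1 gives 2:1 allocation. Then 35 × 2/3 ≈ 23 on etrasimod and 35 × 1/3 ≈ 12 on placebo. One event is 1/23 = 4.3% or 1/12 = 8.3% of the arm, provided that subject has no other event counted in the same table row. The arm sizes are also assumed: not all 35 need enrol, and SAP 8.2 says central randomization did not control balance among Japanese subjects.

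**The case against.** The best defence is that Section 18.1 carries the definition and Appendix 2 only settles onset timing when dates are incomplete. No text says the appendix overrides the section, so a careful programmer could apply the worsening rule first. That is possible, and the documents do not show that the exclusion was ever programmed. But Section 18.1 sends flag assignment for partial dates to this table, the table gives a definite answer, and the answer is wrong under the definition. A plan should not rely on the programmer noticing.

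A second defence is data capture. Protocol 9.8.8.1.1 counts pre-existing conditions that worsen among adverse events, so sites might enter a worsening as a new record with its own onset date. The protocol does not say that they do. Protocol 9.8.8.1.5 has severity assessed at onset and the maximum severity recorded with the outcome of that event, which points to a single record. The worsening exception in the known-date row would also be unnecessary if every worsening were a new record.

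Three points on the other side stand, and they limit the conclusion.

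- **The event is not lost from the report.** It remains in the all-AE listing, and reasons for stopping treatment are summarised separately (SAP Section 10) without reference to TEAE status.
- **The integrated analysis is separate.** SAP Sections 4 and 18.1 plan a combined APD334-302/308 analysis under its own plan, which is not in these documents. Section 18.1.5 places the special-interest rates with confidence intervals and rate differences there.
- **Other rows of Appendix 2 lean the other way.** An unworsened event with a missing start date, or a partial one that could be on or after the dose, is counted as a TEAE if it stopped later or has no stop date.

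**Conclusion.** The contradiction is real and can be read directly from the SAP: Appendix 2 gives Not TEAE for a worsened event that Section 18.1 and the adjacent known-date row make a TEAE. The effect is limited to TEAE summaries and TEAE-specific listings under this SAP.

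A reader might infer three stronger things that the documents do not support.

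- **That about one event is lost.** Multiplying 20 to 30 carry-over events by 5% gives 1 to 1.5, but that counts all carry-over events with partial start dates. Only those that also worsened are misclassified. On the assumptions above the expected number is 0.1 to 0.45, so zero is the likeliest outcome.
- **That the error always favours etrasimod.** The row applies to both arms. It can only lower an arm's TEAE count, but a placebo event lost this way would make etrasimod look worse by comparison.
- **That every TEAE table in the programme is affected.** The integrated analysis has its own plan and cannot be judged here.

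This is a minor point, worth correcting because the plan gives two answers for the same event and a single event weighs visibly in arms this small.

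**What to change.** In SAP Appendix 2, change the action for a partial start date that must precede the first APD334-308 dose to: Not TEAE, unless the event worsened (increase in severity) on or after the first dose date in APD334-308, then TEAE.

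This brings the row into line with Section 18.1 and the known-start-date row. One detail should be settled at the same time. The general definition in Section 18.1 includes worsening on the day of the first dose, while the known-date row and the carry-over sentence speak only of worsening after it. The same wording should be used in all three places.

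The cost is one clause in the appendix and one condition in the TEAE flag program. It needs no new data, and no other classification tested above changes.

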APPENDIX 3. IBDQ SCORING RULES

The IBDQ is a 32-item self-administered questionnaire which has 4 dimensions: Bowel symptoms (10 items), systemic symptoms (5 items), emotional health (12 items), and social function (5 items). Responses are graded on a 7-point Likert scale where 7 denotes “not a problem at all” and 1 denotes “a very severe problem”. Scores range from 32 to 224, a higher score indicates better quality of life.

The 4 dimensions are defined as:

Bowel symptoms: Questions 1, 5, 9, 13, 17, 20, 22, 24, 26, 29

Systemic symptoms: Questions 2, 6, 10, 14, 18

Emotional health: Questions 3, 7, 11, 15, 19, 21, 23, 25, 27, 30, 31, 32

Social function: Questions 4, 8, 12, 16, 28

APPENDIX 4. SF-36 DOMAIN SCORES

The SF-36 is a 36-item self-administered questionnaire which has 8 scales: Physical functioning (10 items), role limitations due to physical health (4 items), role limitations due to emotional problems (3 items), energy/fatigue (4 items), emotional wellbeing (5 items), social functioning (2 items), pain (2 items), and general (5 items). Each item response is scored from 0 to 100 and items in the same scale are averaged together to create 8 subscores. Scores range from 0 to 100. A higher score indicates a more favorable health state.

The 8 dimensions are defined as:

Physical functioning: Questions 3-12

Role limitations due to physical health: Questions 13-16

Role limitations due to emotional problems: Questions 17-19

Energy/fatigue: Questions 23, 27, 29, 31

Emotional wellbeing: Questions 24-26, 28, 30

Social functioning: Questions 20, 32

Pain: Questions, 21, 22

General health: Questions 1, 33-36

APPENDIX 5. WPAI-UC SCORING RULES

The WPAI-UC questionnaire was developed to measure the effect of general health and symptom severity on work productivity and regular activities. The questionnaire includes the following questions.

Questions:

- 1 = Are you currently employed?
- 2 = During the past seven days, how many hours did you miss from work due to your problems associated with UC?
- 3 = During the past seven days, how many hours did you miss from work because of any other reasons?
- 4 = During the past seven days, how many hours did you actually work?
- 5 = During the past seven days, how much did your UC affect your productivity while you were working?
- 6 = During the past seven days, how much did your UC affect your ability to do your regular daily activities, other than work at a job?

Derivation:

- 1) Calculate work time missed score as: $Q2/(Q2+Q4)$
- 2) Calculate impairment while working score as: $Q5/10$
- 3) Calculate overall work impairment score as: $Q2/(Q2+Q4) + [(1 - Q2/(Q2+Q4)) \times (Q5/10)]$
- 4) Calculate activity impairment score as: $Q6/10$

Multiply each score by 100 in order to express as percentages.

